3. SYNOPSIS

INVESTIGATIONAL PRODUCT	
Name of Investigational Product (IP)	BAX69 (imalumab), a fully human recombinant anti-oxidized macrophage migration inhibitory factor (anti-oxMIF) antibody
Name(s) of Active Ingredient(s)	BAX69 (imalumab)
CLINICAL CONDITION(S)/INDICATION(S)	
Metastatic colorectal cancer (mCRC)	
PROTOCOL ID	391401
PROTOCOL TITLE	A Phase 2a Randomized, Open-Label Study to Assess the Safety, Tolerability, and Efficacy of BAX69 in Combination with 5-FU/Leucovorin or Panitumumab versus Standard of Care in Subjects with Metastatic Colorectal Cancer
Short Title	Phase 2a Study of BAX69 and 5-FU/Leucovorin or Panitumumab versus Standard of Care in Subjects with Metastatic Colorectal Cancer
STUDY PHASE	Ph2a
PLANNED STUDY PERIOD	
Initiation	Q2 2015
Primary Completion	Q4 2016
Study Completion	Estimated study completion will occur when 75% of overall survival (OS) events are reported.
Duration	Approximately 21 months
STUDY OBJECTIVES AND PURPOSE	
Study Purpose The purpose of this study, in subjects with progressive measurable mCRC, is as follows: 
• To evaluate the safety and tolerability of imalumab in combination with 5-fluorouracil (5-FU)/leucovorin (LV) or panitumumab to determine the recommended phase 2 dose (RP2D) of each combination• To compare the efficacy of imalumab in combination with 5-FU/LV versus standard of care (SoC) (investigator choice) as third or fourth treatment line in subjects with KRAS mutated (mut) and/or NRAS mut tumors• To compare the efficacy of imalumab in combination with panitumumab versus SoC (investigator choice) as third or fourth treatment line in subjects with KRAS wild type (wt) and NRAS wt tumors Furthermore, the pharmacokinetic (PK) profile of imalumab in combination with 5-FU/LV or panitumumab will be characterized, and limited pharmacodynamic (PD) serum markers will be explored.	
Primary Objectives 
1. To determine the RP2D of imalumab in combination with 5-FU/LV or panitumumab (Part 1)2. To compare progression-free survival (PFS) between imalumab in combination with 5-FU/LV for subjects with KRAS mut and/or NRAS mut tumors or in combination with panitumumab for subjects with KRAS wt and NRAS wt tumors, versus SoC (investigator choice) as third or fourth treatment line (Part 2)	

Secondary Objectives	

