8.2.3 Definition of Dose-Limiting Toxicity

A DLT is defined as any drug-related treatment-emergent adverse event (TEAE) (graded according to the National Cancer Institute Common Terminology Criteria for Adverse Events [NCI CTCAE] v4.03) that occurs during the first 28 days after treatment start and that meets any of the following criteria:

- Any \geq Grade 3 non-hematologic toxicity excluding:
 - a. Mucositis/stomatitis of Grade 3 that resolves to Grade 1 or less with supportive measures within 7 days
 - b. Diarrhea of < 3 days duration following adequate and optimal therapy

- c. Nausea and vomiting of < 3 days duration with adequate and optimal therapy
- d. Fatigue of < 7 days duration following initiation of adequate supportive care
- e. Alopecia
- f. Any single laboratory value out of the normal range that has no clinical significance and that resolves to \leq Grade 2 with adequate measures within 7 days; transient Grade 3 elevations (lasting < 5 days) of hepatic transaminases in the absence of simultaneous increase in serum bilirubin
- Any Grade 4 hematologic toxicity excluding:
 - a. Grade 4 neutropenia lasting for \leq 5 days and not associated with fever
 - b. Isolated Grade 4 lymphocytopenia without clinical correlate
- Grade 3 febrile neutropenia
- Grade 3 thrombocytopenia associated with bleeding
- Any life-threatening complication or abnormality not covered in the NCI CTCAE v4.03

In subjects treated with panitumumab, if a dermatologic reaction develops that is Grade 3 (NCI CTCAE v.4.03) or higher (or is considered intolerable), the dose modifications recommended in the product label will be implemented.³⁴

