12.1.1.2 Suspected Unexpected Serious Adverse Reaction (SUSAR)

Any suspected adverse reaction to study treatment (ie, including active comparators) that is both serious and unexpected.

The event(s) must meet all of the following

- Suspected adverse reaction
- Serious
- Unexpected
- Assessed as related to study treatment

Once determined to meet the criteria for a SUSAR, an SAE should be submitted to regulatory agencies expeditiously.

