12.1.1.4 Unexpected Adverse Events

An unexpected adverse event is an AE whose nature, severity, specificity, or outcome is not consistent with the term, representation, or description used in the Reference Safety Information (RSI) (eg, IB, package insert). The expectedness of AEs will be determined by the sponsor using the IB as the RSI. This determination will include considerations such as the number of AEs previously observed, but not on the basis of what might be anticipated from the pharmacological properties of a medicinal product.

For the purposes of this study, all AEs experienced by a subject, including unexpected AEs, will be recorded on the AE CRF.

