12.1.2.2 Causality

Causality is a determination of whether there is a reasonable possibility that the IP is etiologically related to/associated with the AE. Causality assessment includes, eg, assessment of temporal relationships, dechallenge/rechallenge information, association (or lack of association) with underlying disease, presence (or absence) of a more likely cause, and physiological plausibility. For each AE, the investigator will assess the causal relationship between the IP and the AE using his/her clinical expertise and judgment according to the following most appropriate algorithm for the circumstances of the AE:

- Not related (both circumstances must be met)
 - Is due to underlying or concurrent illness, complications, concurrent treatments, or effects of concurrent drugs
 - Is not associated with the IP (ie, does not follow a reasonable temporal relationship to the administration of IP or has a much more likely alternative etiology)
- Unlikely related (either 1 or both circumstances are met)
 - Has little or no temporal relationship to the IP
 - A more likely alternative etiology exists
- Possibly related (both circumstances must be met)
 - Follows a reasonable temporal relationship to the administration of IP
 - An alternative etiology is equally or less likely compared to the potential relationship to the IP
- Probably related (both circumstances must be met)
 - Follows a strong temporal relationship to the administration of IP, which may include but is not limited to the following:
 - Reappearance of a similar reaction upon re-administration (positive rechallenge)
 - Positive results in a drug sensitivity test (skin test, etc.)
 - Toxic level of the IP as evidenced by measurement of the IP concentrations in the blood or other bodily fluid
- Another etiology is unlikely or significantly less likely

For events assessed as not related or unlikely related and occurring within 5 days, the investigator shall provide the alternative etiology. These causality definitions will also be used to assess the relationship of an AE with a study-related procedure(s), if necessary.

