13.2 Datasets and Analysis Cohorts

The Safety Population is defined as all subjects who receive at least 1 administration of IP. The Safety Population will be used for all safety analyses in the trial.

The Full Analysis Set (FAS) will serve as the population for the analyses of efficacy data in the trial. The FAS will include all subjects who 1) received at least 1 administration of IP, and 2) have 1 post-baseline tumor response assessment based on RECIST v1.1 or died within 18 weeks of the start of treatment.

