5.2 Handling of Missing, Unused, and Spurious Data

Regarding missing data in AE records:

- Handling of unknown causality assessment:
 - If a subject experiences an AE with a missing causality assessment, the relationship of the AE will be counted as “related”.
- Handling of unknown toxicity grades:
 - If a subject experiences more than one AE categorized under the same preferred term, the subject will be counted under the most severe toxicity grade reported for that AE.
 - If a subject experiences an AE and the toxicity grade was not provided, the toxicity grade of this AE should be counted as “unknown”. A row or column labelled “Unknown” should be inserted for those AEs in tables where AEs are summarized by toxicity grade.

For lab values that are above or below the limit of quantitation and are reported as “<” or “>” the assay limit, the assay limit will be used for calculation of summary statistics, except for PK parameters which will be specified in a separate document.

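### Causality is assessed only against imalumab, while the DLT count, the SUSAR rules and the treatment-related AE tables rely on relatedness to a wider object that is never reconciled with it

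*Protocol*

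**What the plan says.** - **Object of causality.** Protocol 12.1.2.2: "Causality is a determination of whether there is a reasonable possibility that the IP is etiologically related to/associated with the AE". Section 12.1.2 asks for the relationship to IP exposure or a study procedure, and 12.1.2.3 refers again to the investigational product. The Synopsis names the IP as "BAX69 (imalumab), a fully human recombinant" antibody. No section asks for causality to 5-FU/LV, panitumumab or an SoC drug.
- **Categories.** 'Not related' needs two circumstances together. The first is: "Is due to underlying or concurrent illness, complications, concurrent treatments, or effects of concurrent drugs". The second is absence of association with the IP. 'Unlikely related' needs only one of two circumstances, and a more likely alternative cause is one of them. 'Possibly related' still applies when the alternative is no more likely than the IP. Protocol 13.4.4.2 and SAP 8.3 analyse 'unlikely related' as not related.
- **DLTs.** Protocol 8.2.3: "A DLT is defined as any drug-related treatment-emergent adverse event (TEAE"), with no drug named. Section 7.2 makes the RP2D of each combination a primary objective. Section 13.4.3.1 requires fewer than 33% of evaluable subjects with a DLT.
- **SUSARs.** Protocol 12.1.1.2: "Any suspected adverse reaction to study treatment (ie, including active comparators) that is both serious and unexpected". Section 12.1.1.4: "The expectedness of AEs will be determined by the sponsor using the IB as the RSI".
- **Analysis.** SAP 8.3 (Table 3) plans treatment-related TEAE tables by study cohort, and SAP 5.4 (Table 1) lists the SoC groups as cohorts. SAP 5.2: "If a subject experiences an AE with a missing causality assessment, the relationship of the AE will be counted as" related. Protocol 13.2: "The Safety Population is defined as all subjects who receive at least 1 administration of IP". SAP 4.2 says study drug instead.

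**The concern.** The primary safety outcome concerns a combination, but the only causality rule considers one of its components. A Grade 3 event that the investigator thinks more likely due to the partner drug fails the relatedness test of 12.1.2.2. A site that takes 'drug-related' to mean any study drug counts it as a DLT. A site that applies 12.1.2.2 does not. The same event can thus enter or leave the DLT count, and Part 1 cohorts are small enough for one event to matter.

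In Part 2, Arm B never receives the IP. If 12.1.2.2 is followed literally, the related-event columns for SoC in the SAP tables reflect how sites fill in an inapplicable field. The SUSAR definition needs an assessment of relatedness to comparators, which the algorithm does not supply, and expectedness is then judged from the imalumab brochure.

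**Working it through.** The plan states no figure on this point, so there is none to reproduce. The check sets the passages side by side and then looks at the cohort arithmetic.

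**1. Related to what?**

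| Place | Object |
|---|---|
| Protocol 12.1.2, 12.1.2.2, 12.1.2.3 | IP (12.1.2 adds study procedure) |
| Protocol 8.2.3 and Synopsis, SAP 2 (DLT) | 'drug', not named |
| Protocol 12.1.1.2 (SUSAR) | study treatment, comparators included |
| Protocol 13.4.4.2 (AE tables) | the treatment |
| SAP 8.3 | study drug; SAP 5.3 dates first administration from imalumab or SoC |

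Only the first row has an algorithm behind it.

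**2. A partner-drug event under 12.1.2.2**

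- Partner drug more likely than imalumab: 'unlikely related', analysed as not related.
- Partner drug equally likely, timing reasonable: 'possibly related', analysed as related.
- 'Not related' requires a cause such as a concurrent drug and also no association with the IP.

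The route out of the related count is therefore 'unlikely related'.

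**3. What one event does** (Protocol 8.2.1.1 and 13.4.3.1)

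- First dose level: 0/3 = 0% opens the second level after DRC review. 1/3 = 33.3% adds three subjects.
- 1/6 = 16.7% meets <33%. 2/6 = 33.3% does not.

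**4. Illustration on assumed rates**

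The documents give neither the regimen's rate of DLT-type events, p, nor the share f set aside as partner-drug toxicity. Both are assumed. I also assume that the DRC passes a level at 1/6. The counted rate is q = p(1 − f), and

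P(pass) = (1 − q)³ + 3q(1 − q)² × (1 − q)³.

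For p = 0.33:

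- f = 0: q = 0.33; 0.67³ + 0.99 × 0.67⁵ = 0.30076 + 0.13366 = 0.434.
- f = 0.5: q = 0.165; 0.835³ + 0.495 × 0.835⁵ = 0.58218 + 0.20093 = 0.783.

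| p | f = 0 | f = 25% | f = 50% | f = 75% |
|---|---|---|---|---|
| 20% | 71% | 81% | 91% | 97% |
| 33% | 43% | 61% | 78% | 93% |
| 40% | 31% | 49% | 71% | 91% |
| 50% | 17% | 35% | 60% | 86% |

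The chance of 0/3 alone would not serve as the chance of moving on, because a cohort with 1/3 expands to six and the DRC may still escalate.

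**5. Arm B**

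Arm B is planned at 22 of 66 subjects. If every relationship field were entered as 'not related', 0% of its AEs would be related. If every field were blank, the missing-data rule would make it 100%. These are bounds, not forecasts.

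**The case against.** The strongest reply is that 8.2.3 cites neither the IP nor 12.1.2.2. A regimen reading of 'drug-related' has support: 10.3.3.1 uses study drugs in the plural to cover 5-FU/LV and panitumumab, and 13.4.4.2 relates events to the treatment. The DRC sets the RP2D on the full data of evaluable subjects (8.2.1), so it would see partner-drug events. Only imalumab is escalated, and setting aside toxicity clearly due to a fixed-dose partner is an arguable choice. On Arm B, SAP 4.2, 5.3 and 8.3 refer to study drug or SoC, AEs are summarised descriptively, and nothing says that the field would be left blank. The AE CRF is not among the documents and may already collect causality per drug. Section 12.1.2.2 also asks for the alternative cause of some unrelated events, so partner attribution is partly captured.

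Much of this stands, and it limits the point to an unreconciled definition. It does not remove it:

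- These passages show that a wider reading is possible. None says that it applies to the DLT definition.
- The <33% criterion is numerical, so DRC discretion does not settle which events are counted.
- The sentence in 8.2.3 on Grade 3 or higher skin reactions with panitumumab does not say whether they are DLTs.
- The alternative cause is requested only for events within 5 days.
- Section 12.1.1.4 mentions package inserts as an example of reference safety information, but then makes the brochure the basis for expectedness.

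**Conclusion.** The point holds as an unreconciled definition that reaches the primary safety outcome. Causality is collected against imalumab alone, while DLTs, SUSARs and the treatment-related tables need a wider object. Toxicity more likely due to the partner drug may be left out of the DLT count, and Arm B relatedness cannot be interpreted if 12.1.2.2 is followed literally. The firm part of the size is that one event separates 0/3 from 1/3 and 1/6 from 2/6. The probabilities above rest on assumed p and f and on passing at 1/6, and show direction only.

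A reader might infer four stronger things that the documents do not support:

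- *Partner-drug events are by definition 'not related'.* That category needs both circumstances, and an equally likely partner cause stays 'possibly related'.
- *Partner toxicity is certainly lost from the DLT count.* This depends on how 'drug-related' is read.
- *Arm B relatedness has no meaning anywhere in the plan.* This is true of the 12.1.2.2 algorithm, but the SAP wording allows a study-treatment reading.
- *Comparator SUSARs cannot be identified.* The CRF cannot be checked, and comparators are expressly in scope.

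**What to change.** - **Protocol 12.1.2.2 and the AE CRF** (if not already so): record causality separately for imalumab, 5-FU/LV, panitumumab and the assigned SoC drug. Add a 'not applicable' entry for products not given, so that they do not fall under the missing-counts-as-related rule.
- **SAP 8.3:** define 'related' as related to any assigned study treatment, in the same way for both arms.
- **Protocol 12.1.1.2 and 12.1.1.4:** reconcile them by naming the reference safety information for each product.
- **Protocol 13.2:** align the Safety Population with SAP 4.2 so that Arm B is included. Say how subjects on best supportive care alone are handled, since they receive no drug.
- **DLT definition:** Protocol 8.2.3, 10.3.3.1, 12.1.1.2 and 12.1.2.2 and SAP 8.3 must be reconciled so that the object of 'drug-related' is stated. Which rule is right is for the sponsor and its clinical advisers. SAP 5.4 already gives 10 mg/kg for Part 2, so the report should also list Part 1 events of DLT grade by attribution, letting readers see whether the reading mattered.

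The cost is a few CRF fields, one listing and wording changes. The reported related-event rate may look less favourable.

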12.1.2.3 Safety Reporting

Adverse events/SAEs will be assessed at all study visits as outlined in the Schedules of Study Procedures and Assessments (see [Table 3](#), [Table 4](#), and [Table 5](#)) and Section [12.1.2](#).

Adverse events/SAEs are to be recorded on the AE page of the eCRF. Each event should be recorded separately.

Any SAE, including death due to any cause, which occurs during this study, whether or not related to the investigational product, must be reported immediately (within 24 hours of the study center's first knowledge of the event). All SAEs must be reported via the Electronic Data Capture (EDC) system by completing the relevant eCRF page(s) in English. Once the SAE has been recorded in the EDC system, the sponsor and other designated recipients will be informed of the event automatically. For instances in which the EDC may become unavailable, SAEs must be reported using the back-up paper SAER Form to meet the 24 hour timeline requirement (for contacts and instructions refer to the SAER Form). Once the EDC becomes available, the site must enter all SAE data as reported on the back-up paper SAER Form on the applicable eCRF pages.

The reported event will contain as much available information concerning the SAE to enable the sponsor or designee to file a report, which satisfies regulatory reporting requirements. The initial SAE information reported on the applicable eCRF pages (or back-up SAER Form, if applicable) must at least include the following:

- Protocol Number
- Subject identification number and demographics (gender, age at onset of event and/or date of birth)
- Investigational product exposure
- Medical Term for Event (Diagnosis preferably)
- Description of the (S)AE, including:
 - Date of onset
 - (S)AE treatment (drug, dose, route of administration)
 - Causal relationship by the Investigator
 - Measures taken (ie, action taken regarding investigational product in direct relationship to the AE)
 - Outcome
- Seriousness criteria (ie, death, life-threatening, or other criterion)

- Cause of death
- Autopsy findings (if available)
- Name, address, fax number, email, and telephone number of the reporting Investigator (for paper SAER Forms)

The serious adverse event reporting contact information is provided below by country:

Country	Telephone	Fax
Germany	PPD	PPD
Spain	PPD	PPD
United Kingdom	PPD	PPD
United States	PPD	PPD

Criteria for documenting the relationship to the investigational product, severity, and outcome will be as described in Section 12.1.

All SAEs that are spontaneously reported within 30 days of a subject's last visit are to be collected and reported as previously described.

In medical emergencies, the investigator should use medical judgment and remove the subject from the immediate hazard. The sponsor or designee will be notified regarding the type of emergency and course of action taken and the procedures for SAE reporting will be followed, if necessary.

During a subject's participation in the study, the investigator or institution will provide adequate medical care for any AEs, including clinically significant laboratory values related to the study. The investigator or institution should inform a subject when medical care is needed for an intercurrent illness (clinic, laboratory results, or otherwise) that in the opinion of the investigator should receive medical follow-up.

12.2 Urgent Safety Measures

An urgent safety measure is an immediate action taken, which is not defined by the protocol, in order to protect subjects participating in a clinical trial from immediate harm.

Urgent safety measures may be taken by the sponsor or clinical investigator and may include any of the following:

- Immediate change in study design or study procedures
- Temporary or permanent halt of a given clinical trial or trials
- Any other immediate action taken in order to protect clinical trial participants from immediate hazard to their health and safety

The investigator may take appropriate urgent safety measures in order to protect subjects against any immediate hazard to their health or safety. The measures should be taken immediately and may be taken without prior authorization from the sponsor. In the event(s) of an apparent immediate hazard to the subject, the investigator will notify the sponsor immediately by phone and confirm notification to the sponsor in writing as soon as possible, but within 1 calendar day after the change is implemented. The sponsor will also ensure the responsible ethics committee (EC) and the relevant competent authorities are notified (in writing, if applicable) of the urgent safety measures taken in such cases according to local regulations.

12.3 Untoward Medical Occurrences

Untoward medical occurrences occurring before the first exposure to IP are not considered AEs (according to the definition of AE, see Section 12.1). However, each **serious** untoward medical occurrence experienced before the first IP exposure (ie, from the time of signed informed consent up to but not including the first IP exposure) will be described on the AE CRF (and SAER Form if eCRF is not available). These events will not be considered as SAEs and will not be included in the analysis of SAEs.

For the purposes of this study, each non-serious untoward medical occurrence experienced by a subject undergoing study-related procedure(s) before the first IP exposure will be recorded on the AE CRF; these events will not be considered as AEs and will not be included in the analysis of AEs.

